#### **5.4.1.1.8. HBeAg Cut-offs**

The cut-offs for HBeAg level are as follows:

- $\geq$ LLOQ
- < LLOQ (0.11 IU/mL)

#### **5.4.1.1.9. HBV DNA Cut-offs**

The cut-offs for HBV DNA are as follows:

- < LLOQ for target detected and not detected
- < LLOQ for target not detected
- < LLOQ for target detected
- <60 IU/mL
- <100 IU/mL
- <200 IU/mL
- <1000 IU/mL
- <2000 IU/mL
- <20000 IU/mL

#### **5.4.1.1.10. Suppressed HBV DNA**

HBV DNA < LLOQ (HBV DNA detectable or HBV DNA TND) and HBV DNA < 60 IU/mL will be evaluated over all time points when assessed with emphasis at FU Weeks 12, 24, 36 and 48 (i.e. 12, 24, 36, 48 weeks after completion of all study interventions at Week 24), and without restarting NA treatment.

#### **5.4.1.1.11. ALT Normalization**

ALT elevation at baseline is defined as  $ALT \geq ULN$ . A participant with ALT elevation at baseline achieves ALT normalization if his/her ALT value post-baseline is <ULN at any given time point.

Participants who achieve ALT normalization on treatment and off treatment but without restarting NA treatment will be evaluated over time.

Participants who were retreated with NA and who have  $ALT \geq ULN$  before NA re-treatment and reach ALT normalization after NA re-treatment during follow-up will be evaluated.

Additionally, for those participants who restarted NA treatment during the follow-up, the participants who reach  $ALT < ULN$  and who have ALT less than their nadir value will be evaluated.

#### **5.4.1.1.12. Partial Cure**

Partial cure will be evaluated at each of the following time points separately: FU Week 12, 24, 36 and 48. A participant will be defined as having achieved partial cure if he/she has:

- Stopped all study interventions at any time, and
- had HBV DNA level  $< 2,000$  IU/ml at the given follow-up week of interest, and
- had HBsAg  $\geq LLOQ$  at the given week of interest, and
- not required NA re-treatment after stopping all study interventions.

Of note, HBV DNA level  $< 2,000$  IU/ml may be achieved prior to the week of interest but must be observed at the given week of interest.

#### **5.4.1.1.13. Virologic Breakthrough**

HBV virological breakthrough is defined as having a confirmed on-treatment HBV DNA increase by  $>1 \log_{10}$  from nadir level (lowest level reached during treatment) in participants who didn't have on-treatment HBV DNA level below the lower limit of quantification (LLOQ) or a confirmed on-treatment HBV DNA level  $>200$  IU/mL in participants who had on-treatment HBV DNA level below the lower limit of quantification (LLOQ). Confirmed HBV DNA increase/level means that the criterion should be fulfilled at 2 or more consecutive time points or at the last observed time points or at the last observed on-treatment time point. On-treatment will be defined as the time period in which the participant receives any of the study interventions (including NA).

In addition, participants who experience a virologic breakthrough followed by on-treatment biochemical flare will be evaluated.

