Assessments and sampling include efficacy (eg, HBsAg, HBeAg, and HBV DNA), safety (eg, [S]AEs, labs, ECGs, vital signs, physical examinations), PK, PK/ PD, viral genome sequencing, PBMC, human leukocyte

^a Kim BK, Revill PA, Ahn SH, et al. HBV genotypes: relevance to natural history, pathogenesis and treatment of chronic hepatitis B. *Antiviral Therapy*. 2011;16:1169-1186

antigen (HLA) typing, immunogenicity and pharmacogenomic samples, blood sampling for exploratory analysis of host and viral markers, and medical resource utilization.

The total duration of individual participation will be up to 72 weeks (screening not included). Participants will be considered to have completed the study if they have completed all the assessments of the end of study (EOS) visit (ie, FU Week 48).

An internal Data Review Committee (DRC) will be commissioned for monitoring safety of participants enrolled in this study. In addition, an Independent Flare Expert Panel (IFLEP) will be appointed.

NA Re-treatment Criteria During Follow-up

Participants who meet the protocol-defined NA treatment completion criteria (based on the Week 24 or FU Week 2 results) will be monitored closely during the follow-up period with a study visit at least once every 4 weeks. They should re-start NA treatment immediately in the event of:

- Signs of decreasing liver function based on laboratory findings (eg, International Normalized Ratio [INR], direct bilirubin) or clinical assessment (eg, ascites, hepatic encephalopathy).
- HBV DNA value of >1,000,000 IU/mL (irrespective of confirmation and/or ALT increase).

Note: A post-treatment HBV DNA value of >100,000 IU/mL should trigger re-testing of ALT/AST, HBV DNA, and total and direct bilirubin within a maximum of 7 days from receipt of the data and further repeats as necessary (ie, weekly until HBV DNA returns to <100,000 IU/mL). A post-treatment HBV DNA value of >20,000 IU/mL (but <100,000 IU/mL) should trigger a re-test within 14 days. At all times, additional re-testing of the above parameters should be performed at the investigator's discretion.

In addition, re-start of NA treatment should be considered in the following cases:

- Confirmed post-treatment HBeAg seroreversion (HBeAg positive after it was negative at NA completion), OR
- Confirmed (at least 4 weeks apart) post-treatment increases in HBV DNA >2,000 IU/mL and ALT >5x upper limit of normal (ULN), OR

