6.5.1. NA Treatment Completion

All participants will receive the last dose of JNJ-3989 at Week 24 and the last dose of PegIFN- α 2a at Week 23 (Arms 1 and 2) or Week 11 (Arm 3). They will start the FU Period after the Week 24 visit. If all of the following NA treatment completion criteria are met based on the Week 24 results, treatment with NA will be stopped at the next scheduled visit (ie, FU Week 2):

- The participant has ALT <3x ULN, AND
- The participant has HBV DNA <60 IU/mL at Week 24 and HBV DNA <LLOQ at the previous visit, or HBV DNA <LLOQ at Week 24, AND
- The participant is HBeAg-negative, AND
- The participant has HBsAg <100 IU/mL.

Note: Participants who are close to meeting the protocol-defined NA treatment completion criteria with the Week 24 results, and do meet the criteria based on the FU Week 2 results may be allowed to stop NA at FU Week 4, after consultation with the Sponsor. In case of ALT elevation \geq 3x ULN at Week 24, the investigator must consider different potential causes of increased ALT to ensure appropriate work up and management as needed. If the ALT elevation is unrelated to HBV activity and/or <3x ULN by FU Week 2, NA completion may be considered at the discretion of the investigator and in consultation with the sponsor.

Participants who do not meet the above criteria based on the Week 24 or FU Week 2 results should continue NA treatment during the 48-week FU Period.

Participants who meet the above-mentioned NA treatment completion criteria will be monitored closely during the 48-week FU Period with a study visit at least once every 4 weeks. NA treatment should be re-started in accordance with the NA re-treatment criteria (see Section [6.5.2](#), NA Re-treatment Criteria During Follow-up, for more details).

The investigator should consider to re-start NA treatment per local standard of care at the EOS visit (Follow-up Week 48) for participants who met the NA treatment completion criteria based on the Week 24 (or FU Week 2) results, who did not re-start NA treatment during the follow-up phase, and who did not achieve and maintain HBsAg seroclearance. NA will not be provided by the sponsor after the final study visit.

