ISR	injection site reaction
KPD	kinetic pharmacodynamic model
LLN	lower limit of normal
LLOQ	lower limit of quantification
MDSC	myeloid-derived suppressor cell
MoA	mode of action
MRI	magnetic resonance imaging
MRU	medical resource utilization
NA	nucleos(t)ide analog
NIMP	non-investigational medicinal product
NK	natural killer
NOAEL	no observed adverse effect level
PBMC	peripheral blood mononuclear cell
PD	pharmacodynamic(s)
PegIFN- α 2a	pegylated interferon alpha-2a
pgRNA	pre-genomic ribonucleic acid
PK	pharmacokinetic(s)
PoC	proof of concept
Q4W	every 4 weeks
QW	weekly
QD	once daily
QTcF	QT interval corrected for heart rate according to Fridericia's formula
RBC	red blood cell
rcDNA	relaxed circular deoxyribonucleic acid
RNAi	ribonucleic acid interference
SAE	serious adverse event
SAP	Statistical Analysis Plan
SD	standard deviation
SDM	site-directed mutant
SE	standard error
siRNA	small interfering ribonucleic acid
$t_{1/2\text{term}}$	terminal half-life
T4	thyroxine
TAF	tenofovir alafenamide
TEAE	treatment-emergent adverse event
t_{max}	time to reach C_{max}
TND	target not detected
TNF	tumor necrosis factor
TSH	thyroid stimulating hormone
WBC	white blood cell

Definitions of Terms

ALT/AST nadir	Lowest ALT/AST value during study participation
End of study intervention (EOSI)	Time of the last administration of study intervention
Functional cure (FC)	HBsAg seroclearance at 24-weeks after EOSI
HBsAg or HBeAg seroclearance	HBsAg or HBeAg negativity, respectively, based on the assay used
HBsAg or HBeAg seroconversion	HBsAg or HBeAg negativity and anti-HBs or anti-HBe antibody positivity, respectively
IC ₅₀	half maximal inhibitory concentration
Study intervention	JNJ-73763989 (JNJ-3989), NA (either ETV, tenofovir disoproxil, or TAF), and PegIFN- α 2a
Virologic breakthrough	Confirmed on-treatment HBV DNA increase by $>1 \log_{10}$ IU/mL from nadir or confirmed on-treatment HBV DNA level >200 IU/mL in participants who had HBV DNA level $<$ LLOQ of the HBV DNA assay.

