- 1 (Yes) = confirmed\*\* ALT and/or AST  $\geq 3x$  ULN and  $\geq 3x$  nadir (i.e. lowest value observed up to the start of the flare)
- 0 (No) = otherwise

**4. Clinical flare** is defined as follows:

A clinical flare occurs either when a virologic flare and biochemical flare overlap in time or when a biochemical flare starts within 4 weeks following the end of a virologic flare. The start date of a clinical flare is defined as the minimum start date of the virologic flare and the biochemical flare. The end date of a clinical flare is defined as the maximum end date of the virologic flare and biochemical flare, i.e., the later date of HBV DNA returns to  $\leq 200$  IU/mL and 50% reduction from the peak ALT and/or AST level.

- 1 (Yes) = confirmed\*\* HBV DNA > peak threshold and confirmed\*\* ALT and/or AST  $\geq 3x$  ULN and confirmed\*\*  $\geq 3x$  nadir (i.e. lowest value during study participation).

- 0 (No) = otherwise

\*\* Confirmed means that the criterion should be fulfilled at 2 or more consecutive time points or at the last observed time point.

The virologic and clinical flares will be assessed only off-treatment, while biochemical flares will be identified on-treatment and off-treatment. On-treatment virologic flares are described as virologic breakthrough in Section 5.4.1.1.13. On-treatment will be defined as the time period in which the participant receives any of the study interventions. Off-treatment will be defined as the period after stopping all study interventions (including NA).

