#### 5.7.4.1. Time Points and Samples

When analyzing sequencing data, the focus will be on genetic variants at

- Time Point of Sequence at Virologic Breakthrough: time point with sequence data available closest to the time point of virologic breakthrough (FTPT) (See Section 5.4.1.1.13 for virologic breakthrough definition)
- Time Point of Sequence at Virologic Flare: time point with sequence data available closest to the time point of Virologic flare (See Section 5.4.1.1.14 for virologic flare definition)
- Time Point of Sequence at Re-treatment during Post-treatment Follow-up: time point with sequence data available closest to time point where re-treatment criteria is met (See Section 5.4.1.1.1)
- Aggregated Post-Baseline Study Period (ASSEQ): entire post-baseline study period, aggregate of all available time points in the study with sequence data available
- Aggregated Post-Baseline Treatment Period (ATSEQ): entire post-baseline treatment period, aggregate of all available post-baseline time points during the treatment phase with sequence data available

Given only participants who are on stable NA treatment and who have HBV DNA <60 IU/mL at screening will be enrolled in this study, no baseline sequencing can be performed. In the exceptional case baseline HBV DNA levels are above the sensitivity limit of the sequencing assay used, the baseline sample may be sequenced.

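### Virologic breakthrough re-opens when NA is restarted in follow-up, with no renewed suppression required, so an off-NA rebound still above 200 IU/mL can be scored a second time as breakthrough

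*SAP*

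**What the plan says.** SAP 5.4.1.1.13 has two branches. A participant never below LLOQ on treatment needs a confirmed rise of more than 1 log10 from nadir. The branch above 200 IU/mL applies "in participants who had on-treatment HBV DNA level below the lower limit of quantification (LLOQ". Confirmation means two or more consecutive time points, or one value "at the last observed on-treatment time point". The window is set by this sentence: "On-treatment will be defined as the time period in which the participant receives any of the study interventions (including NA". Protocol Appendix 1 lists the study interventions as "JNJ-73763989 (JNJ-3989), NA (either ETV, tenofovir disoproxil, or TAF" and PegIFN-α2a, so NA counts.

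SAP 5.4.1.1.14 uses the same window for flares ("On-treatment will be defined as the time period in which the participant receives any of the study interventions"). It ends a virologic flare when HBV DNA returns to 200 IU/mL or below, or at NA restart if that is earlier. It also says that an on-treatment virologic flare is what 5.4.1.1.13 calls breakthrough.

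On stopping NA, the HBV DNA criterion in Protocol 6.5.1 is met by a value below 60 IU/mL at Week 24 with "HBV DNA <LLOQ at the previous visit, or HBV DNA <LLOQ at Week 24". On restarting, Protocol 6.5.2 names three HBV DNA levels: above 2,000 IU/mL with ALT above 5x ULN (confirmed), above 20,000 IU/mL (confirmed), and "HBV DNA value of >1,000,000 IU/mL (irrespective of confirmation and/or ALT increase".

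**The concern.** Breakthrough is meant to show loss of suppression while treatment is being taken. A rebound that began off NA and is still clearing after restart is a different event, yet nothing in 5.4.1.1.13 separates the two. The LLOQ condition looks back to any earlier on-treatment value and is not renewed at restart.

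The protocol objective is breakthrough throughout the study, so follow-up counts are part of the endpoint. Follow-up rows would mix restart carry-over with true loss of suppression in participants who never stopped NA. The label then passes to breakthrough followed by on-treatment biochemical flare, to the sequencing tables (SAP 5.7.4.1 uses the "time point with sequence data available closest to the time point of virologic breakthrough (FTPT"), and to the DRC summaries in SAP Table 10.

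**Working it through.** The documents state no breakthrough, restart or decline rate, so there is no plan figure to reproduce. The check is whether the stated rule scores carry-over, and under what conditions.

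**Step 1: eligibility.** A participant who stops NA under Protocol 6.5.1 had HBV DNA below LLOQ at Week 24 or the visit before, or at the equivalent FU Week 2 assessment, while on NA. The LLOQ condition for the 200 IU/mL branch is therefore already met, and 5.4.1.1.13 does not ask for it again.

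**Step 2: distance from the cut-off.** 2,000/200 = 10, 20,000/200 = 100 and 1,000,000/200 = 5,000. The falls needed to reach 200 IU/mL are log10 of these: 1.00, 2.00 and 3.70.

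**Step 3: decline that avoids the label.** HBV DNA must be at or below 200 IU/mL by the second on-NA time point, or by the only one if it is also the last. Required rate = fall / weeks to that time point, in log10 per week:

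| Restart level (IU/mL) | Fall | 4-weekly visits (second at week 8) | Single last value at week 4 | Weekly re-tests (second at week 2) | 12-weekly visits (second at week 24) |
|---|---|---|---|---|---|
| 2,000 | 1.00 | 0.125 | 0.25 | 0.50 | 0.04 |
| 20,000 | 2.00 | 0.25 | 0.50 | 1.00 | 0.08 |
| 1,000,000 | 3.70 | 0.46 | 0.92 | 1.85 | 0.15 |

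The weekly column applies where Protocol 6.5.2 triggers weekly re-tests (HBV DNA above 100,000 IU/mL or ALT above 5x ULN), and only if those samples count as time points under SAP 5.1.3. The single-value column is the restart close to FU Week 48.

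**Step 4: the literal rule on hypothetical courses.** Restart at 2,500, 25,000 or 1,100,000 IU/mL was crossed with assumed declines of 0.15, 0.25, 0.5 and 1.0 log10 per week, with 4-weekly visits. Four of 12 courses are scored as breakthrough: the two higher levels at 0.15 and 0.25. For example, 25,000 falling at 0.25 gives 2,500 at week 4 and 250 at week 8, so it is scored; at 0.5 it gives 250 and then 2.5, so it is not. If renewed HBV DNA below LLOQ is required after restart, none of the 12 is scored.

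**Step 5: size in one arm.** For 34 participants and no true breakthrough (Clopper-Pearson 90% CI):

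| Re-scored rebounds | Proportion | 90% CI |
|---|---|---|
| 0 | 0% | 0 to 8.4% |
| 1 | 2.9% | 0.2 to 13.2% |
| 3 | 8.8% | 2.4 to 21.3% |
| 5 | 14.7% | 6.0 to 28.5% |

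**Step 6: time to breakthrough.** SAP 5.4.1.3.4 censors non-events at or before EOT but does not limit events to EOT. Suppose 31 of 34 are censored at day 169 and restart events fall at days 280, 308 and 336. The risk sets are 3, 2 and 1, and Kaplan-Meier cumulative incidence is 1 - 2/3 = 33%, 1 - (2/3)(1/2) = 67%, then 100%. A single post-EOT event, with everyone else censored at EOT, also gives 100%.

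**The case against.** The best defence is that the text contains the effect. SAP 5.4.2.1.13 tabulates breakthrough by analysis phase, so treatment-period rows cannot hold restart carry-over. SAP 5.4.1.3.4 censors at EOT, and SAP 5.4.1.2.1 uses on-treatment nadir for the first 24 weeks, which suggests that a window closing at Week 24 was intended. SAP 5.1.3 keeps extra visits out of the summaries, though it allows them for clinically important endpoints, so weekly re-tests may not count. Sequencing at virologic flare and at re-treatment is already listed apart from breakthrough, and SAP 5.7.4.5 suppresses frequency outputs with fewer than 5 participants.

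Most of this stands as a limit on size. It does not remove the defect: 5.4.1.1.13 expressly includes NA, the follow-up rows remain exposed, and the competing windows show that the SAP has not settled which one applies.

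Three stronger readings are tempting and are not supported:

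- A reader might infer that every HBV-DNA-driven restart becomes a breakthrough. Steps 3 and 4 show that it depends on level, decline and visit spacing.
- A reader might infer that the endpoint would consist mainly of re-treated rebounds, or be highest in the arm with the best HBsAg response. NA stopping does require HBsAg below 100 IU/mL, but the documents give no rates of stopping, restart or breakthrough.
- A reader might infer that the same ALT episode is certain to be counted twice. An off-treatment biochemical flare already runs through restart to its own ALT/AST end date, and no text says that it also opens an on-treatment flare. That is an ambiguity, not a stated rule.

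**Conclusion.** The point holds for HBV DNA. Read as written, SAP 5.4.1.1.13 and 5.4.1.1.14 together can close one rebound as an off-treatment virologic flare at restart and score its remainder as breakthrough. This needs HBV DNA above 200 IU/mL at two consecutive on-NA time points, or at the last one. It is less likely after low or fast-clearing rebounds, and more likely after high ones, with weekly re-tests that count as time points, or with a restart near FU Week 48.

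The size rests on assumed decline rates and on an unknown number of restarts; the per-arm figures illustrate and do not forecast. The reach is limited to breakthrough proportions for follow-up and for the whole study, the sequencing and DRC summaries keyed to breakthrough, and the time-to-breakthrough curve. A correction should be made before database lock, but it does not bear on the trial's main conclusion.

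**What to change.** 1. In SAP 5.4.1.1.13, state that an NA restart in follow-up resets both the nadir and the LLOQ condition. HBV DNA above 200 IU/mL then counts as breakthrough only after HBV DNA has again been below LLOQ on the restarted NA. Viraemia continuing from before the restart belongs to the off-treatment virologic episode and opens no new event.
2. In SAP 5.4.1.1.14, add that an ALT/AST episode that began off treatment is counted once, as an off-treatment flare up to its existing end date, and does not also open an on-treatment flare.
3. In SAP 5.4.1.3.4, give events and censoring the same window: since non-events are censored at or before EOT, count only events up to EOT.

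Response to restarted NA keeps its own exploratory endpoint, so no information is lost. The cost is SAP wording and derivation code. No data collection, visit schedule or re-treatment rule changes.

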#### **5.4.1.1.14. Flares**

The criteria based on blood markers/lab tests for each of the flare types are defined as below.

**1. Virologic flare** is defined as follows:

Virologic flare will be assessed only for those participants who are off-treatment.

The start of a confirmed virologic flare is defined as the first date of two consecutive visits with HBV DNA  $>200$  IU/mL. The end date of the same confirmed virologic flare is defined as the first date when HBV DNA value returns to  $\leq 200$  IU/mL or the date of NA treatment restart, whichever

comes first. Each virologic flare will be categorized based on the confirmed (i.e. two consecutive values) peak HBV DNA above any of the three thresholds within the start and end date of that flare as follows: 20,000 IU/mL 2,000 IU/mL and 200 IU/mL.

- 1 (Yes) = confirmed\*\* HBV DNA > peak threshold.
- 0 (No) = at least one off-treatment HBV DNA measurement available and not meeting the criteria of confirmed HBV DNA > peak threshold.
- 2 (Not applicable) = no off-treatment HBV DNA quantitative measurements available.

**2. Off-treatment Biochemical flare** is defined as follows:

The start date of a confirmed off-treatment biochemical flare is defined as the first date of two consecutive visits with ALT and/or AST  $\geq 3x$  ULN and  $\geq 3x$  off-treatment nadir (i.e. lowest value observed during off-treatment period up to the time point of meeting the biochemical flare criteria) while the participant does not receive any of the study interventions. The end date of the same off-treatment biochemical flare is defined as the first date when there is a 50% reduction from the peak ALT and/or AST level &  $< 3x$  ULN.

- 1 (Yes) = confirmed\*\* ALT and/or AST  $\geq 3x$  ULN and  $\geq 3x$  nadir (i.e. lowest value observed up to the start of the flare)
- 0 (No) = otherwise

**3. On-treatment Biochemical flare** is defined as follows:

The start date of a confirmed on-treatment biochemical flare is defined as the first date of two consecutive visits with ALT and/or AST  $\geq 3x$  ULN and  $\geq 3x$  on-treatment nadir (i.e. lowest value observed on-treatment period up to the time point of meeting the biochemical flare criteria) while the participant receives any of the study interventions. The end date of the same on-treatment biochemical flare is defined as the first date when there is a 50% reduction from the peak ALT and/or AST level &  $< 3x$  ULN, regardless of stopping the study interventions.

- 1 (Yes) = confirmed\*\* ALT and/or AST  $\geq 3x$  ULN and  $\geq 3x$  nadir (i.e. lowest value observed up to the start of the flare)
- 0 (No) = otherwise

**4. Clinical flare** is defined as follows:

A clinical flare occurs either when a virologic flare and biochemical flare overlap in time or when a biochemical flare starts within 4 weeks following the end of a virologic flare. The start date of a clinical flare is defined as the minimum start date of the virologic flare and the biochemical flare. The end date of a clinical flare is defined as the maximum end date of the virologic flare and biochemical flare, i.e., the later date of HBV DNA returns to  $\leq 200$  IU/mL and 50% reduction from the peak ALT and/or AST level.

- 1 (Yes) = confirmed\*\* HBV DNA > peak threshold and confirmed\*\* ALT and/or AST  $\geq 3x$  ULN and confirmed\*\*  $\geq 3x$  nadir (i.e. lowest value during study participation).

- 0 (No) = otherwise

\*\* Confirmed means that the criterion should be fulfilled at 2 or more consecutive time points or at the last observed time point.

The virologic and clinical flares will be assessed only off-treatment, while biochemical flares will be identified on-treatment and off-treatment. On-treatment virologic flares are described as virologic breakthrough in Section 5.4.1.1.13. On-treatment will be defined as the time period in which the participant receives any of the study interventions. Off-treatment will be defined as the period after stopping all study interventions (including NA).

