6.5.2. NA Re-treatment Criteria During Follow-up

Participants who meet the protocol-defined NA treatment completion criteria based on the Week 24 (or FU Week 2) results should complete NA treatment at FU Week 2 (or FU Week 4) as outlined in Section 6.5.1, NA Treatment Completion, and will be monitored closely during the follow-up period with a study visit at least once every 4 weeks. They should re-start NA treatment immediately in the event of:

- Signs of decreasing liver function based on laboratory findings (eg, International Normalized Ratio [INR], direct bilirubin) or clinical assessment (eg, ascites, hepatic encephalopathy).
- HBV DNA value of $>1,000,000$ IU/mL (irrespective of confirmation and/or ALT increase).

Note: A post-treatment HBV DNA value of $>100,000$ IU/mL should trigger re-testing of ALT/AST, HBV DNA, and total and direct bilirubin within a maximum of 7 days from receipt of the data and further repeats as necessary (ie, weekly until HBV DNA returns to $<100,000$ IU/mL). A post-treatment HBV DNA value of $>20,000$ IU/mL (but $<100,000$ IU/mL) should trigger a re-test within 14 days. At all times, additional re-testing of the above parameters should be performed at the investigator's discretion.

In addition, re-start of NA treatment should be considered in the following cases:

- Confirmed post-treatment HBeAg seroreversion (HBeAg positive after it was negative at NA completion), OR
- Confirmed (at least 4 weeks apart) post-treatment increases in HBV DNA $>2,000$ IU/mL and ALT $>5x$ ULN, OR

Note: A post-treatment ALT value of $>5x$ ULN should trigger re-testing of ALT, AST, ALP, total and direct bilirubin, INR, albumin, and HBV DNA on a weekly basis until ALT and AST levels have returned to $<5x$ ULN. At all times, additional re-testing of these parameters should be performed at the investigator's discretion.

- Confirmed (at least 4 weeks apart) post-treatment increases in HBV DNA $>20,000$ IU/mL.

The decision to re-start NA treatment should take into consideration the dynamics of HBsAg, HBV DNA and/or ALT values and should be discussed with the Sponsor.

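### SAP 5.4.1.1.14 confirms a virologic flare in two ways that do not agree, so a fast HBV DNA rebound cut short by NA restart can be under-graded or scored as no flare

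*SAP*

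**What the plan says.** SAP 5.4.1.1.14 builds a virologic flare in three steps.

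- **Start.** "The start of a confirmed virologic flare is defined as the first date of two consecutive visits with HBV DNA" above 200 IU/mL.
- **End.** The first value of 200 IU/mL or less "or the date of NA treatment restart, whichever" is earlier.
- **Category.** 20,000, 2,000 or 200 IU/mL, according to the "confirmed (i.e. two consecutive values) peak HBV DNA above any of the three thresholds within the start and end date of that flare".

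The Yes/No line under the category then points to a footnote: "Confirmed means that the criterion should be fulfilled at 2 or more consecutive time points or at the last observed time point". The section limits virologic flares to the time after all study interventions, including NA, have been stopped.

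Two other SAP sections bear on this. Section 5.4.1.3.5 dates time to first off-treatment flare from the earlier of two confirming visits. Section 5.4.1.1.13, on virologic breakthrough, allows confirmation "or at the last observed on-treatment time point". The flare footnote has no matching off-treatment qualifier.

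For participants who have stopped NA, Protocol 6.5.2 says: "They should re-start NA treatment immediately in the event of" signs of falling liver function or an HBV DNA value above 1,000,000 IU/mL, the latter "irrespective of confirmation and/or ALT increase".

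**The concern.** The protocol's most urgent virologic trigger acts on a single value. The SAP's start date and grade need two, and the flare is closed when NA restarts. The value that prompts restart can therefore be the last one off NA, with nothing to pair it with. This touches only rebounds fast enough to reach 1,000,000 IU/mL between visits, which are the ones a flare summary most needs to get right.

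Frequency of virologic and/or biochemical flares in those who met the NA completion criteria is a named secondary endpoint. The Amendment 1 summary gives as its trigger a severe flare after NA discontinuation in another study, with HBV DNA rising rapidly before liver markers changed. An error here would bias flare incidence and severity downward. It would also carry into clinical flare, which requires a virologic flare, and into time to first flare.

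**Working it through.** The documents give no expected flare rate or rate of HBV DNA rise, so there is no plan figure to reproduce. The check applies the SAP rule to short test series and then asks how fast a rebound must be to be affected.

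**Inputs.** Flare start above 200 IU/mL, end at NA restart, categories 200 / 2,000 / 20,000 (SAP 5.4.1.1.14). Restart on one value above 1,000,000 and visits at least every 4 weeks off NA (Protocol 6.5.2). Blood drawn before study drug at visits (Schedule of Activities, note b). The value 1,500,000 is illustrative.

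**Step 1: classification.** The last off-NA value is 1,500,000 IU/mL, then NA restarts and HBV DNA is suppressed.

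| Previous off-NA value | Two consecutive off-NA values | Footnote = last off-NA value, also used for the grade | Footnote = last value in the study |
|---|---|---|---|
| 150 | no flare | >20,000 | no flare |
| 1,500 | >200 | >20,000 | >200 |
| 15,000 | >2,000 | >20,000 | >2,000 |
| 50,000 | >20,000 | >20,000 | >20,000 |

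If a pre-dose sample at the restart visit is also high, the first row becomes >20,000 even under the two-value wording, provided the restart date counts as inside the flare. The SAP does not say whether it does.

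**Step 2: speed needed.** To pass 1,000,000 within 28 days from a value f, the rise is log10(1,000,000/f) and the doubling time is at most 28 × ln 2 / ln(1,000,000/f):

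- f = 200: 3.70 log10, about 2.3 days
- f = 2,000: 2.70 log10, about 3.1 days
- f = 20,000: 1.70 log10, about 5.0 days

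**Step 3: chance of jumping a threshold.** Assume a log-linear rise of g log10 per week, 4-weekly visits, no plateau, and a crossing time uniform between visits. The chance that the first value above T already exceeds 1,000,000 is max(0, 1 − (6 − log10 T)/(4g)).

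- T = 20,000 (category too low, or no flare): 1 − 1.70/2.0 = 15% at g = 0.5; 1 − 1.70/4.0 = 58% at g = 1.0; 1 − 1.70/6.0 = 72% at g = 1.5
- T = 200 (no flare at all): 0%; 1 − 3.70/4.0 = 8%; 1 − 3.70/6.0 = 38%

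These are conditional on a participant reaching 1,000,000 IU/mL. They ignore any second sample taken before restart. A participant stopping NA at FU Week 2 has a first gap of 2 weeks, which lowers the chance.

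**Step 4: weight of one case.** One misclassified participant is 1/34 = 2.9 percentage points of an arm. Among those who actually stop NA the denominator is smaller and not stated.

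**The case against.** A reader might infer that the SAP always demands two off-NA values, that the trigger value can never be confirmed, and that the most severe rebounds are therefore systematically lost. The documents do not support that.

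- The footnote accepts a single value at the final time point. Since virologic flares are assessed only off treatment, this can fairly be read as the last off-NA value, which resolves the Yes/No score. The contrast with the breakthrough definition is weak evidence of intent: that definition lists both a general last time point and an on-treatment one, which looks like loose drafting.
- A second value may exist. Any HBV DNA above 100,000 IU/mL calls for a re-test within 7 days, and a visit to collect NA allows a pre-dose sample. A previous value above 20,000 IU/mL also gives the right category.
- The start-date sentence does not itself say that both visits must be off NA.
- The cases remain visible. SAP 5.4.2.1.3 tabulates each re-treatment sub-criterion and actual restarts, and biochemical flares are counted on and off treatment.

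What this does not answer: the grade sentence carries its own two-value definition and is confined to the flare dates. The two-visit start date and the time-to-flare rule are likewise not cured by a generous reading of the footnote. Participants who restart NA stay in follow-up, so the literal last time point is usually on NA. The re-test may fall after an immediate restart, and NA may be dispensed ahead to someone with a pending confirmation who cannot attend.

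Two further inferences also fail. An open-ended top category at 20,000 IU/mL is a choice, not an error; bands at 100,000 and 1,000,000 would be a preference. Nor is the clinical flare necessarily lost when ALT rises after restart: the SAP already counts a biochemical flare starting within 4 weeks of the end of a virologic flare, and restart is one such end. The remaining doubt is the statement that clinical flares are assessed only off treatment.

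**Conclusion.** The point holds as an unresolved inconsistency in an endpoint definition. Two programmers following SAP 5.4.1.1.14 could classify the same rebound differently, from no flare to the top category. Under the two-value reading, or with the footnote taken as the last value in the study, the error runs one way: too few or too mild. It does not arise if the footnote means the last off-NA value and also governs the grade, if a second pre-restart sample is available and counted, or if the previous value was already above 20,000 IU/mL.

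The number of participants affected cannot be estimated from the documents. The 15%, 58% and 72% figures rest on assumed growth rates and show only that the problem is confined to fast rebounds. The endpoint is descriptive, without multiplicity control, so no hypothesis test of the primary endpoint is at risk. It should still be corrected, because flares after stopping NA are a named secondary endpoint and the correction is cheap.

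**What to change.** In SAP 5.4.1.1.14, define confirmation once: the criterion is met at two consecutive off-treatment time points, or at the last off-treatment value on or before NA restart, with a pre-dose sample on the restart day counted as off-treatment. Apply it to the flare start date, the Yes/No score and the peak category, and align time to first virologic flare in 5.4.1.3.5. Under this wording all four series in the table are scored >20,000.

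Also state that a biochemical flare starting within the existing 4-week window after NA restart counts toward a clinical flare, even though the participant is by then on NA.

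The cost is SAP wording and programming. The downside is that a few flares resting on one value will be counted. This concerns classification only and implies no change to the clinical restart rule.
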